9.3.1 LV Thickness-Dimension Ratio (LV T-D)

The primary endpoint of this trial is LV thickness-dimension ratio (LV T-D) z-score. LV thickness is reported in terms of LV posterior wall dimension in systole, while LV dimension will be based on the internal diameter in diastole. Z-scores will be calculated using the formula: $(LVPWD / LVEDD - 0.18) / 0.025$.²¹

LV T-D Z-score will be determined at baseline, 6 months, 12 months, 18 months and 24 months. The z-scores will be appropriately transformed to normality as necessary. The analysis will be conducted accounting for correlation among repeated measurements within individuals. This may be done using the Generalized Estimating Equation (GEE) approach or by the restricted maximum likelihood estimation (REML) approach with the mixed effect model with random effects. Various covariance structures will be assumed, including the unstructured, compound symmetry, and autoregressive lag-1 correlation. GEE and REML will be implemented using GENMOD and MIXED procedures in SAS.

LV T-D z-scores will be modeled as a linear function of time. Under the intention-to-treat principle, the efficacy of carvedilol will be examined by comparing the slopes of the longitudinal linear models of LV T-D z-score between carvedilol and placebo control group. The difference in slopes by treatment group will be introduced by including an interaction term of time with group indicator (0 for placebo, 1 for carvedilol). Treatment effect will be tested by a 1-df test for the interaction. Non-linear effects will be tested by including an interaction of a quadratic term in time with the group indicator.

To examine other than the linear model, we will also fit an unstructured mean model, which is a non-parameterized model with four indicator variables of time. Interactions of the time and group indicators will be included to allow for treatment differences at follow-up time points. This will enable us to examine other than linear or quadratic trends in time.

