Because of randomization, we expect no difference between the expected values of LV T-D z-scores at t0 between the treatment groups. However, we will evaluate the success of the randomization by examining between-group differences in demographic and clinical characteristics (i.e. age at anthracycline exposure, chest radiation, time from treatment), study site, as well as the mean LV T and D z-scores at baseline. If imbalance is evident, our analysis will take into account the covariates with significant imbalance.

Low dose carvedilol will be considered effective if the 1-df test in the linear model is significant and the expected LV T-D z-score is lower for placebo at follow-up

time points, indicating the effectiveness of low-dose carvedilol in preserving LV T-D.

In addition to unadjusted analyses which are appropriate under the randomization principle, adjusted analysis will also be performed. Significantly imbalanced covariates and covariates known to be prognostic for HF, such as age at anthracycline exposure, chest irradiation, and time from completion of treatment, will be incorporated in the longitudinal models before including and testing the time by treatment group interaction.

To address potential noncompliance, we will also conduct an as-treated analysis, considering patients' actual treatment uptake. Instead of the treatment indicator (placebo or carvedilol), we will include adherence rate, i.e. 0 for placebo and a number between 0 and 1 for carvedilol determined by pill count, in the linear mixed effects model. Time-specific adherence rate and the overall adherence rate will be considered. If carvedilol is effective, we may expect to see an increase in LV T-D z-score and a greater difference in slope with increasing adherence rate.

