The longitudinal power calculations were conducted using the program RMASS2.¹²⁹ We assumed a Type I error of 0.05, power of 0.80, 2-sided test, linear trend, and compound symmetry correlation matrix ($[\rho]$ ranging from 0.6 to 0.9). An attrition rate of 19% per arm/year (voluntary withdrawal, discontinuation due to drug intolerance, unexpected events [pregnancy/ relapse]) was assumed. Table 4 shows the minimum effect size at 24 months that can be detected for a given correlation between measures. For example, with 91 individuals in each group, we have 80% power to detect a difference of at least 0.38 in LV T-D z-score between the two arms if the correlation between baseline and the 2 year LV T-D z-score is 0.6. With regards to the secondary endpoints of efficacy, 3-6 mL increases in LVESV, 6-10 mL increases in LVEDV, or 3-5% drops in LV EF (from normal resting LV EF) have been associated with adverse cardiovascular outcomes in clinical trials with patients with preserved or mildly depressed EF.¹³⁰⁻¹³² Thus, effect sizes presented in Table 4 are plausible and clinically meaningful.

Secondary Aim – Establish safety and tolerability of the two-year course of carvedilol.

ACTIVATION PROTOCOL:

Adverse events: We assume the rate of Grade 2-4 toxicities in the placebo group to be low, at 5%. At the end of the study, assuming 88 individuals remaining in each arm (15% attrition/year from the original 125/ arm), the study will have at least 80% power to detect

an adverse event rate of 19.2% in the carvedilol group based on Fisher's exact test and Type I error=0.05.

Adherence to therapy: We will examine the difference in adherence rates by comparing the percent adherence by treatment group. With 125 study participants at baseline per arm, assuming a constant adherence rate of 90% in the placebo group, a between-measurement correlation of 0.6, 15% yearly attrition, and 2-sided alternative, there will be 80% power to detect an adherence rate of 75% in the carvedilol group.

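### The success rule in Section 9.3.1 judges significance on slope but direction on level; the two can disagree if the arms have separate baseline means

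*Combined protocol and SAP*

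**What the plan says.** Section 9.3.1 sets the efficacy question as "comparing the slopes of the longitudinal linear models of LV T-D z-score between carvedilol and placebo control group". On the model it says: "The difference in slopes by treatment group will be introduced by including an interaction term of time with group indicator". On the test: "Treatment effect will be tested by a 1-df test for the interaction". The decision rule follows. Carvedilol counts as effective when "the 1-df test in the linear model is significant and the expected LV T-D z-score is lower for placebo at follow-up". The section does not say whether follow-up here means all four visits (6, 12, 18 and 24 months) or the last one, and it does not ask for the slope difference itself to be positive.

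On baseline, the same section says "Because of randomization, we expect no difference between the expected values of LV T-D z-scores at t0 between the treatment groups". It plans to compare the arms at baseline, including the LV means, and adds: "If imbalance is evident, our analysis will take into account the covariates with significant imbalance".

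Section 9.4 (Amendment #4) bases power on a two-sided 0.05 test of a linear trend: "with 91 individuals in each group, we have 80% power to detect a difference of at least 0.38 in LV T-D z-score" at correlation 0.6. Appendix II, Table s3, gives one-sided bounds for the same interaction test, with a final bound of 1.960 (nominal p 0.025).

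**The concern.** The claim is about slope, that is, preservation of the ratio over two years. Direction, however, is read from the fitted level at follow-up, and in a model with separate arm intercepts that level carries whatever baseline difference randomisation leaves.

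- If placebo happens to start higher, carvedilol can have a clearly better slope while placebo's fitted mean is still higher at 6 months. Read as requiring every visit, the rule then fails.
- If carvedilol happens to start higher, its slope can be significantly worse while its fitted mean stays above placebo's. With a two-sided test, the rule then passes.

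This sentence decides the primary conclusion. The stated 80% power belongs to the slope test, not to the two-part rule.

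**Working it through.** **Inputs.** 91 per arm, 1:1; SD 1.0; visits at 0, 6, 12, 18 and 24 months; compound symmetry with correlation 0.6 to 0.9 (0.7 observed from baseline to 6 months); 19% attrition per year; two-sided 0.05; projected 24-month difference 0.4 (Sections 9.2, 9.3.1 and 9.4).

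**Step 1: reproduce Table 4.** For a linear contrast with attrition, the detectable difference is (1.960 + 0.842) × √(2 c′DVDc) ÷ (c′t/2). Here t is time in years (0, 0.5, 1, 1.5, 2), c is centred time, V is the correlation matrix and D is diagonal with entries 1/√n_t, where n_t = 91 × 0.81^t.

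| Correlation | 0.6 | 0.7 | 0.8 | 0.9 |
|---|---|---|---|---|
| Table 4 | 0.38 | 0.34 | 0.28 | 0.21 |
| Recomputed | 0.380 | 0.333 | 0.278 | 0.208 |

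The plan's figures reproduce, and they describe the slope test only.

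**Step 2: why level and slope can disagree.** Under linearity a 24-month difference of 0.4 is 0.4 × 6/24 = 0.1 at 6 months. The standard error of a chance baseline difference is √(2/91) = 0.148, larger than the effect expected at that visit.

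Worked case, correlation 0.7, separate intercepts, generalised least squares with monotone dropout: SE of the intercept difference 0.140, SE of the 24-month slope difference 0.120, correlation between the two −0.342. The fitted 6-month difference is the intercept difference plus one quarter of the 24-month slope difference. Its variance is 0.140² + 0.25² × 0.120² + 2 × 0.25 × (−0.342) × 0.140 × 0.120 ≈ 0.0177, so its SE is about 0.133. The chance that it favours carvedilol is Φ(0.1/0.133) ≈ 0.77. With a slope-test probability of 0.914, the product is about 0.71. The exact joint probability is 0.70, because the two estimates are slightly negatively correlated.

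**Step 3: probability of meeting the rule.** Simulation from the bivariate normal distribution of (intercept difference, slope difference), at least 3 million draws per case:

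| Correlation | 0.6 | 0.7 | 0.8 | 0.9 |
|---|---|---|---|---|
| True difference 0.4: slope test, carvedilol favoured | 0.825 | 0.914 | 0.982 | >0.999 |
| Rule, all four visits | 0.635 | 0.702 | 0.751 | 0.757 |
| Rule, 24 months only | 0.824 | 0.913 | 0.979 | 0.996 |
| Loss, all visits, with non-significant baseline difference | 0.166 | 0.188 | 0.207 | 0.218 |
| Table 4 difference: slope test | 0.785 | 0.808 | 0.811 | 0.851 |
| Rule, all four visits | 0.592 | 0.585 | 0.553 | 0.541 |
| Rule, 24 months only | 0.784 | 0.804 | 0.796 | 0.795 |

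At 0.4 the all-visits loss is 19 to 24 points, of which 17 to 22 arise when the baseline difference is not significant at 0.05. The figures at 0.4 barely change (63%, 70%, 75%, 76%) if retention instead falls linearly to 62%, which matches the 56 of 91 completers assumed in Section 9.4.

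**Step 4: passing on an unfavourable slope (two-sided test, separate intercepts).** At a true harm of 0.2 the probability is 0.4%, 0.9%, 2.2% and 5.9% across the four correlations. At a true harm of 0.4 it is 0.1% to 0.4%. With no effect it is 0.2% to 0.6%. If the final statistic must exceed +1.960, as in Table s3, it is zero.

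**Step 5: common baseline mean.** The fitted arm difference at time t is then the slope difference multiplied by t. It is positive at every visit exactly when the slope difference is positive, so both problems vanish.

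**The case against.** The strongest reply is that the plan intends a common baseline. Section 9.3.1 names only the time-by-group term and no group main effect. Its unstructured-mean model adds interactions to allow arm differences at follow-up. The section expects equal means at baseline, and Section 9.4 repeats this. On that reading the direction clause is simply the sign of the slope. This stands as a plausible reading, but the plan never says it. Table 4 fits separate intercepts somewhat better: full least squares gives 0.39 and 0.34 at correlation 0.6 and 0.7, against 0.35 and 0.32 with a common baseline, where the table has 0.38 and 0.34. That speaks to the power model and does not settle the analysis model.

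Second, the clause does not say every visit. If 24 months is meant, the loss at 0.4 is negligible (0.1 to 0.4 points), and 0.1 to 5.6 points at the Table 4 differences. This also stands, although the plural leaves the all-visits reading open.

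Third, the section provides for imbalance. It does, but only where imbalance is significant, so it misses most of the loss under the all-visits reading.

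A reader might infer that the rule ignores the slope altogether. It does not: a significant slope test is required, and only its sign is missing. A reader might also infer that the rule readily passes a harmful drug. That needs separate intercepts, a two-sided test and a baseline imbalance larger than the estimated harm, and Table s3's one-sided bound excludes it.

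**Conclusion.** The wording defect is real but minor. Significance and direction are set on different quantities, and whether that matters depends on two things the plan leaves open: common or separate baseline means, and which visits count. Under a common baseline there is no effect. With separate intercepts and all four visits required, the rule is met in about 63% to 76% of trials at the projected 0.4 and about 54% to 59% at the Table 4 differences. With separate intercepts and 24 months only, the loss at 0.4 is at most about 0.4 points.

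The documents do not support an unconditional statement that the trial falls well short of its 80% power. The figures assume compound symmetry, SD 1, known variance, equal true baseline means and monotone dropout of 19% per year. What remains is that one data set could give opposite primary conclusions under permissible readings, which a decision rule should not allow.

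**What to change.** In Section 9.3.1, before the final analysis:

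1. State that carvedilol is effective if the 1-df time-by-group test is significant and the estimated slope difference (carvedilol minus placebo) is greater than 0.
2. Report the fitted arm differences at 6, 12, 18 and 24 months as description, not as a condition.
3. State whether the linear model has a common or a separate baseline mean for the arms.
4. Reconcile the two-sided test in Section 9.4 with the one-sided final bound in Table s3. A two-sided 0.05 test with a positive sign required is the same as exceeding 1.960 at one-sided 0.025, so one sentence suffices.

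This matches the rule to the slope comparison and to the power basis under every reading. It costs a few sentences and needs no new data, patients or procedures.

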9.3.4 Subjective Safety and Tolerability Measures

Treatment adherence. Patients will self-report adherence in the study questionnaires. Compliance will also be measured by pill counts performed every 3 months. The number of pills taken out of the total prescribed in a 3-month period will be modeled as a random effects binomial regression model.¹²⁶ The binomial rates from 8 time points (month 3 to 24) will be modeled as unstructured mean model with 7 indicator variables as well as polynomial models over time. The random-intercept and the random intercept and slope models will be considered. The significance of the time indicators or parameters by treatment interaction will be evaluated for treatment difference in compliance.

Voluntary withdrawals will be examined at the end of the study by comparing the percent of withdrawals between the treatment groups using a chi-square test or Fisher's exact test.

Patient reported symptoms. The outcomes will be scored as a 5-point Likert-type scale (0 to 4) in response to questions on how much the patients are bothered by certain symptoms. The questionnaire will be administered at Days 0, 14, 42 and 90, and every three months after Day 90, for a total of eleven time points. The responses will be treated as normally distributed, as ordinal or dichotomized variable, and we will apply the linear mixed effects model or generalized linear mixed effects model methods to compare changes between treatment groups. Because of additional time points available, in addition to the unstructured mean model, we will also fit piecewise models with join point at 6 months, considering linear and curvilinear trajectories between 6 m and 24 m time points.

Aim 1.2.2: To examine the modifying effects of demographic, clinical, and molecular characteristics on both efficacy and safety markers.

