Health related quality of life will be assessed at baseline and every 6 months during the two-year treatment period (Quality of Life Form and Cardiac Health Questionnaire). The health subscales of the Medical Outcomes Study 36-item Short Form Health Survey (SF-36) is a component of the Quality of Life questionnaire and will be administered to all study participants to assess general and physical health as well as vitality. The

questionnaire has been used in various English-speaking populations ranging from 13 to 74 years of age, representing a wide spectrum of health states (well to seriously ill). The questionnaire has consistently shown strong evidence of internal consistency, stability, convergent and discriminant validity and has been successfully administered in a similar population of childhood cancer survivors evaluated for asymptomatic cardiac dysfunction following anthracycline therapy.^{38,134} Anticipated time to complete HRQL questionnaires is 10 minutes.

Pill counts will be performed to determine adherence to the prescribed intervention using the Adherence Tracking Form. Patient compliance will be assessed by recording the amount of the study drug remaining in returned bottles. Patients will be considered non-compliant if they received < 80% or > 120% of the cumulative prescribed dose for two consecutive periods. Similar cutoffs have been used to determine compliance to study medication in pediatric oncology^{62,63} and non-oncology⁵⁵ randomized cardiac intervention studies. If a patient is found to be < 50% compliant during any 90 day period, they will be removed from the protocol therapy due to non-compliance. Patients should make every attempt to complete the protocol as specified. Investigators should encourage patients to comply with the protocol and return for all scheduled visits.

Pill counts will occur on Days 14, 42, 90, 180, 270, 365, 455, 540, 630, and 730 (see [Section 7.1](#)). On days that coincide with scheduled clinic visits (0, 14, 42, 90, 180, 365, 540, and 730), pill counts will occur in clinic. For non-clinic time-points (270, 455, 630), participants will report pill counts via phone interview. Pill counts for these time points will also be verified at the next in-person study visit.

Compliance will be calculated separately for each bottle of blinded study medication as follows:

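### The supplementary as-treated analysis has no term for patients' own pill-taking, so it is open to healthy-adherer bias, probably small; a randomization-based noncompliance estimate would avoid this

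*Combined protocol and SAP*

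**What the plan says.** Section 9.3.1 makes the randomized comparison primary: "Under the intention-to-treat principle, the efficacy of carvedilol will be examined by comparing the slopes of the longitudinal linear models". Carvedilol is judged effective on the 1-df time-by-arm test, with lower expected z-scores on placebo.

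The same section then adds an as-treated analysis for noncompliance. It drops the arm indicator and puts an adherence score in its place, coded as follows: "0 for placebo and a number between 0 and 1 for carvedilol determined by pill count". On its form: "Time-specific adherence rate and the overall adherence rate will be considered". On what to look for: "If carvedilol is effective, we may expect to see an increase in LV T-D z-score and a greater difference in slope", the latter growing with adherence.

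Pill counts are not limited to one arm. Section 10.7 says: "Pill counts will be performed to determine adherence to the prescribed intervention using the Adherence Tracking Form". Section 9.3.4 models compliance over time as a tolerability outcome and tests it by arm: "The significance of the time indicators or parameters by treatment interaction will be evaluated for treatment difference in compliance". Placebo adherence will therefore be known. No section enters it in the efficacy model, and none plans an instrumental-variable or complier-average analysis.

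**The concern.** Adherence is behaviour after randomization and may go with general health, self-care or tolerability. The planned score varies only within the carvedilol arm. If pill-taking is prognostic, carvedilol patients with high scores do better for that reason, while the same gradient among placebo patients is averaged into a single value at zero. The fitted line through these points slopes upward even when the drug does nothing.

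The time-specific version adds possible reverse causation, because a patient who is getting worse may stop taking capsules.

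At stake is the reading of a supportive result. This is the only analysis of noncompliance planned for the efficacy comparison. If the primary test were null or borderline, an adherence gradient could be offered as support that the model cannot validly give.

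**Working it through.** **Inputs from the documents.** 91 per arm; SD 1.0; visits at 0, 6, 12, 18 and 24 months; compound symmetry; two-sided 0.05; power 0.80; attrition 19% per year; projected 24-month difference 0.4 z (section 9.4). Adherence below 50% in any 90-day period means removal from therapy (sections 8.1 and 10.7). Removed patients need no further evaluations except after a cardiac event or pregnancy (section 8.1).

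**Inputs that are assumptions.** The mean and SD of adherence among carvedilol patients, and the prognostic gradient g (z per year per unit of adherence, the same in both arms). I use g = 0.2 and 0.4, so full versus zero adherence is worth 0.4 or 0.8 z at 24 months.

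**Step 1: the plan's own figure, for scale.** The plan gives no figure for the as-treated model. For the primary slope test:

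- d = (1.960 + 0.842) × √(2 Σᵢ Σⱼ cᵢcⱼrᵢⱼ / √(nᵢnⱼ))
- t is time as a fraction of 24 months; cᵢ = (tᵢ − mean t) / Σ(t − mean t)²; rᵢⱼ = 1 if i = j and ρ otherwise; nᵢ = 91 × 0.81^(years).

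This gives 0.380, 0.333, 0.278 and 0.208 at ρ = 0.6, 0.7, 0.8 and 0.9. Table 4 prints 0.38, 0.34, 0.28 and 0.21. Linear retention (1 − 0.19 × years) gives 0.388, 0.341, 0.285 and 0.217. The design figures reproduce to rounding and are not in dispute.

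**Step 2: bias of the planned score when the drug is inert.** Let a be a patient's adherence (mean m, SD s), X = a on carvedilol and 0 on placebo, with equal arms. The patient's slope is g·a in both arms, apart from a constant. Then:

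- Cov(X, slope) = 0.5·g·E[a²] − 0.5·g·m² = 0.5·g·s²
- Var(X) = 0.5·E[a²] − 0.25·m² = 0.5·s² + 0.25·m²
- bias fraction = 0.5·s² / (0.5·s² + 0.25·m²)

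The spurious 24-month effect is 2g times this fraction. Example, m = 0.80 and s = 0.15: 0.01125 / (0.01125 + 0.16) = 0.066; × 0.4 = 0.026 and × 0.8 = 0.053.

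| m | s | Fraction | Effect, gradient 0.4 z | Effect, gradient 0.8 z |
|---|---|---|---|---|
| 0.90 | 0.10 | 0.024 | 0.010 | 0.019 |
| 0.85 | 0.12 | 0.038 | 0.015 | 0.031 |
| 0.80 | 0.15 | 0.066 | 0.026 | 0.053 |
| 0.80 | 0.20 | 0.111 | 0.044 | 0.089 |
| 0.75 | 0.30 | 0.242 | 0.097 | 0.194 |

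**Step 3: can the widest spread occur?** If every patient analysed has adherence between 0.5 and 1, the largest possible SD is √((1 − m)(m − 0.5)): 0.245 at m = 0.80 and 0.250 at m = 0.75. An SD of 0.30 therefore requires low adherers to stay in the data.

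**Step 4: simulation with an inert drug** (4,000 trials per scenario, 91 per arm, ρ = 0.7, complete visits). At g = 0.4, 24-month effect and two-sided type I error:

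| m, s | Intention to treat | Planned score, all patients | Planned score, below 50% overall contribute nothing | All patients, own adherence × time added in both arms |
|---|---|---|---|---|
| 0.90, 0.10 | 0.000; 0.052 | +0.020; 0.052 | +0.017; 0.048 | 0.000; 0.049 |
| 0.80, 0.20 | −0.003; 0.047 | +0.086; 0.095 | +0.040; 0.060 | −0.003; 0.046 |
| 0.75, 0.30 | 0.000; 0.050 | +0.193; 0.330 | +0.035; 0.059 | −0.001; 0.047 |

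At g = 0.2 with low adherers excluded, the effect is at most 0.020 and type I error at most 0.061. Across all scenarios, adding own adherence keeps the null effect within ±0.003 and type I error between 0.044 and 0.057.

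**The case against.** No decision rests on this analysis. The efficacy rule is the intention-to-treat test, and the supporting evidence for early stopping in Appendix II does not include the as-treated model. This stands, and it limits the point to a supplementary analysis.

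Four stronger readings are tempting, and the documents do not support them.

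- A reader might infer that scoring placebo patients as zero is itself an error. It is not: zero is their correct carvedilol exposure. What is missing is a term for their own pill-taking. Nor does the model set carvedilol adherers against the whole placebo arm; it is a regression, and low-adherence carvedilol patients also sit near zero.
- A reader might infer that the estimate is biased and that an inert drug would show a gradient. That needs adherence to predict the LV T-D slope, and no section says that it does.
- A reader might infer that the plan treats "a greater difference in slope with increasing adherence rate" as proof of efficacy. The sentence is conditional: it says what to expect if the drug works. It does not, however, warn against the converse reading.
- A reader might infer a bias of 0.1 to 0.2 z. Reaching that range needs an adherence spread that the 50% removal rule makes hard to sustain, and an assumed gradient at least as large as the whole projected placebo decline of 0.4 z.

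The objection does not remove the defect. The removal rule limits the bias only incidentally. It works on 90-day periods rather than overall adherence, and removed patients may already have contributed echocardiograms.

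The remedy has limits too. A complier-average estimate largely restates the intention-to-treat test. A model with adherence in both arms still conditions on behaviour that tolerability may alter, and its clean simulated result assumes the same gradient in both arms.

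**Conclusion.** The point holds as a cheap improvement to a supportive analysis. As specified, the as-treated model cannot separate the effect of taking carvedilol from that of being a patient who takes capsules.

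The likely size is modest. Under the assumed gradients of 0.4 to 0.8 z, it is about 0.01 to 0.05 z for tight adherence distributions (SD 0.10 to 0.15). With patients below 50% overall adherence contributing nothing, it is at most about 0.04 z in the scenarios simulated, with type I error about 0.06. That is the largest simulated value, not a mathematical bound. For scale, the detectable differences are 0.21 to 0.38 z. Larger values arise only if many low adherers remain in the analysis.

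All these sizes rest on an assumed spread and gradient, and the time-specific version was not quantified. The primary test, sample size and efficacy rule are unaffected.

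**What to change.** Make the noncompliance analysis a complier-average slope, with randomized arm as the instrument for carvedilol adherence. In its simplest form this is the intention-to-treat slope difference divided by mean carvedilol adherence. State its assumptions: assignment acts only through the drug taken (exclusion restriction), and the effect is proportional to adherence.

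As a supplement, fit observed adherence × time in both arms plus arm × adherence × time. Note that this still conditions on post-randomization behaviour that drug tolerability may affect.

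Label the current coding exploratory, and state that an adherence gradient from it is not evidence of efficacy.

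The cost is SAP wording and one extra supportive model on pill counts already planned. The downside is a wider interval: with mean adherence 0.80 (assumed), the slope and its standard error are both multiplied by about 1/0.80 = 1.25, so the null test stays essentially the intention-to-treat test.
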